If someone is enrolled and not a completer, they would be defined as either 1.) Enrolled, did not select treatment or 2.) Enrolled, selected treatment, did not participate in the post-treatment assessment.

Sub-Study:

We propose to enroll up to up to ~~135~~ ~~180~~ 195 participants in the sub-study to ensure complete data from 117 randomized participants, assuming a 25 - 30% drop-out rate. We will monitor the dropout rate on an ongoing basis, and modify the number of participants recruited as needed to ensure a final sample of N = 117 sub-study completers.

A completer is someone who is enrolled, randomized and participated in at least one data assessment point following randomization.

If someone is enrolled and not a completer, they would be defined as either 1.) Enrolled, not randomized or 2.) Enrolled, randomized, did not provide any data after randomization

Eligibility Criteria

Inclusion criteria:

- (1) Veteran status (defined as prior service in the US Armed Forces and eligible to receive health care services through Veterans Health Affairs);*
- (2) 18 years of age or older; *
- (3) Self-reported presence of chronic pain;**
- (4) Average pain intensity rating of ≥ 3 on a 0-10 Numerical Rating Scale (NRS) of pain intensity in the last week; **
- (5) Worst pain intensity rating of ≥ 5 on a 0-10 Numerical Rating Scale (NRS) of pain intensity in the last week;**
- (6) Duration of chronic pain 3 months or more; **
- (7) Experiences pain at least 75% of the time in the past 3 months; Those who have a hard time answering this question will be asked the following question: "Which statement best describes your pain?"
 - (a) Pain all the time, but the pain intensity varies;
 - (b) Pain most of the time with only occasional periods of being pain-free;
 - (c) Pain that comes and goes;
 - (d) Occasional pain;

Participants must report experiencing pain that matches one of the first two options; **
(8) Able to read, speak, and understand English. **

Exclusion criteria:

- (1) severe cognitive impairment defined as two or more errors on the Six-Item Screener;⁵¹ **
- (2) Current or history of diagnosis of primary psychotic or major thought disorder as listed in participant's medical record or self-reported within the past five years;*
- (3) Hospitalization for psychiatric reasons other than suicidal ideation, homicidal ideation, and/or PTSD self-reported or noted in chart (within the past 5 years);*

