The research staff member, a UW IBIC employee with a Without Compensation (WOC) appointment at the VA, will obtain consent at the IBIC using the UW EEG consent document. They would then collect the EEG activity data, and ask the participant to remain as still as possible during portions of the assessment. The EEG technician will collect from the participant data regarding medication used within 24 hours of assessment. S/he will also ask the participant to rate the intensity of his or her pain just before the assessment (current pain), after a few minutes of the assessment (current pain and worst, least, and average pain over the past few minutes), and at the end of the EEG session (current pain, and worst, least, and average pain over the past few minutes), using 0-10 Numerical Rating Scales. Finally, the technician will ask the participant to think about their chronic pain in general or a particularly painful event for a period of two minutes. The technician will then ask the participant to rate his/her pain intensity, as well as answer some questions about how s/he thought about his/her pain during the two-minute period. The EEG technician then will ask each participant whether they experienced any negative effects they associate with study procedures to make certain all adverse events related to the study are recorded.

The entire brain wave activity assessment will take approximately 45-60 minutes to complete. Participants will be compensated \$100 for completion of the brain wave activity assessment via a check written from the Seattle Institute for Biomedical and Clinical Research (SIBCR). The check will be sent via USPS mail and accompanied by a payment cover letter.

The brain wave activity assessment must be administered at IBIC, and only after completion of the informed consent process. All other assessment activities may be administered at IBIC or a VA site. So, participants have some options around where they do their baseline assessments and in what combination.

Subjects will be asked to complete the same brain activity assessment following completion of treatment following the same procedures above.

The one difference will be, during the post-treatment assessment, participants will complete an additional 10-minute assessment portion in which they think about the skills they learned during the treatment sessions.

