Several sources of information will serve as data for the study, including medical record reviews, self-report assessments, cognitive tests, brain activity assessments, and audio-recorded treatment sessions (to be used for supervision and determination of adherence and fidelity). The study design involves non-invasive procedures.

The data described other than the data collected during the group treatment sessions will be collected solely for research purposes. Participants will be informed that data collected before and after treatment sessions, i.e. data regarding homework practice, pain intensity and comfort before and after each treatment session, and participant engagement as per the study clinician, will be reported in their medical record, as clinically indicated. Research participation will not influence any part of a patient's medical treatment.

E1c. Potential Risks

General/Reaction to Assessments

Regarding research risks, participants may experience fatigue and/or boredom while completing the telephone assessments, cognitive assessment and the treatment sessions. Some participants may also experience mild anxiety, frustration, and/or stress while answering questions about depression, anxiety and PTSD symptoms. As result of answering questions regarding pain and other symptoms, participants may experience a temporary increase in intensity and/or distress of symptoms.

Some participants may also experience mild anxiety, frustration, and/or stress if the cognitive assessment proves difficult for them, and/or during the course of treatment.

Brain Wave Activity Assessments

Some participants may find sitting still for up to one hour (including prep time, adjustment period and actual assessment) and/or wearing an electrode net on their head to be uncomfortable during the EEG assessment. Some participants may also find a temporary increase in their overall pain. Some participants may find the EEG assessment, including questions asked during the EEG, may cause a temporary increase in PTSD symptoms.

Treatment

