The three types of treatment involve discussions and/or exercises about pain and related topics in a group setting that may make some individuals feel uncomfortable. In addition, some individuals may find it uncomfortable or distressing to hear other Veterans discuss their pain or other problems in a group setting. As result of group discussions or exercises, participants may focus more on their pain, which may lead to a temporary increase in pain intensity and/or

distress regarding their pain problem. Some individuals may also experience discomfort (numbness, tingling, perceived loss of sensation) from sitting still for extended periods of time.

Regarding the self-hypnosis training, some individuals may find the state of deep relaxation associated with hypnosis uncomfortable. Also, some individuals under hypnosis may remember past experiences that are uncomfortable and/or cause distress, even after the session has ended. In addition, some individuals under hypnosis or practicing mindfulness may also experience mild disorientation or grogginess during or after the session has ended. No stress or discomfort is anticipated to be associated with the education control intervention, and there is little chance of physical injury from the treatment procedures described above.

Sub-Study: Sleep/Wake Diary

Participants may experience fatigue and/or boredom while completing the sleep/wake diary. Some participants may also experience mild anxiety, frustration, and/or stress while answering questions about sleep and activities during the day.

Sub-Study: Actigraphy Device

Participants may find it uncomfortable or inconvenient in general to wear a device like an actigraph both during the day and while sleeping. There is no risk of electrical shock while wearing the actigraph and it cannot track where participants are or what they are doing. Participants may experience sweating or skin irritation while wearing the actigraph if they have sensitive skin.

Privacy and Confidentiality

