An adverse event (AE) is any untoward medical occurrence in a subject during participation in the clinical study or with use of the experimental agent being studied. An adverse finding can include a sign, symptom, abnormal assessment (laboratory test value, vital signs, electrocardiogram finding, etc.), or any combination of these. Staff will document any occurrence that meets this definition, is a new symptom/condition for the subject, and results in either self-treatment or treatment by a health care provider.

Serious Adverse Event (SAE)

A serious adverse event (SAE) is any AE that results in one or more of the following outcomes:

- Death
- A life-threatening event
- Inpatient hospitalization or prolongation of existing hospitalization
- A persistent or significant disability/incapacity
- A congenital anomaly or birth defect
- An important medical event based upon appropriate medical judgment

As per the VHA Handbook 1058.01 (4.w), an AE is also considered serious when medical, surgical, behavioral, social or other intervention is needed to prevent such an outcome.

Serious Problem

A serious problem is a problem in human research that may be reasonably regarded as [VHA Handbook 1058.01 (4.y)]:

- 1) Involving substantive harm, or a genuine risk of substantive harm, to the safety, rights, or welfare of human research subjects, research staff, or others; or
- 2) Substantively compromising the effectiveness of a facility's human research protection or human research oversight programs.

3b. Classification of AE Severity

AEs will be labeled according to severity, which is based on their impact on the participant. An AE will be termed "mild" if it does not have a major impact on the patient, "moderate" if it causes the patient some minor inconvenience, and "severe" if it causes a substantial disruption to the patient's well-being." Please note that a severe AE and an SAE are distinct terms. A subject could experience a severe AE that does not meet the above-listed definition of an SAE; alternatively, a subject could experience a moderate AE that meets the SAE definition.

All AEs and SAEs that affect clinic patients, i.e. non-research participants, within the clinic context will be addressed by licensed providers conducting the treatment interventions as per VA guidelines.

3c. AE Attribution Scale

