This study will be stopped prior to its completion if: (1) one of the interventions is associated with adverse effects that call into question the safety of the intervention; (2) any new information becomes available during the trial that necessitates stopping the trial; or (3) other situations occur that might warrant stopping the trial.

3i. Designation of a Monitoring Committee

Name/Role*	Credentials	Organization	Expertise
[name]	Ph.D.	Independent Consultant	Biostatistician
[name]	Ph.D.	VAPSHCS	Staff Psychologist
[name]	Ph.D.	VAPSHCS	Clinical Psychologist, Behavioral Interventions/Clinical Trials

The Data Safety Monitoring Committee (DSMC) for this study is comprised of Drs. [name] (chair), [name] and [name]. [name], an independent consultant, has no professional or personal connection with the co-PIs.

Although [name] is employed at the VAPSHCS, she does not collaborate with any of the research team members in a research or clinical capacity on a regular basis. Likewise, although [name] is employed at the VAPSHCS, she does not collaborate with the Co-PIs in a research or clinical capacity on a regular basis.

Drs. [name] and [name] are qualified to review the patient safety data generated by this study because of their unique expertise in the area of randomized controlled trials (RCT) examining the efficacy of psychological interventions in Veteran populations. [name] was selected given his/her expertise in biostatistics.

3j. Methods and Timing for Assessing Recording, and Analyzing Safety Parameters

Monitoring Subject Safety and Study Compliance

Study researchers including staff members and study clinicians who conduct the telephone assessments, brain wave activity assessments, cognitive assessments, and facilitate the treatment groups will collect safety information on an ongoing basis. By systematically monitoring for events, we will ensure that problems are detected immediately and addressed as indicated.

Brain Wave Activity Assessments

The research staff member conducting the assessment will ask each participant following completion of the assessment whether they experienced any negative effects during the assessment they associate with the study procedures. The response to this question will be captured using the EEG Assessment Recording Sheets.

Treatment

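### Section 3a documents an adverse event only if it is new and treated, so non-serious worsening of existing pain, PTSD symptoms or distress (the plan's own named risks) stays out of the AE record, in conflict with the broad AE definition, 3d and D6j

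*Combined protocol and SAP*

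**What the plan says.** Section 3a opens with a wide definition: "An adverse event (AE) is any untoward medical occurrence in a subject during participation in the clinical study". Its last sentence then gives the working instruction. Staff are to document an occurrence that meets the definition, "is a new symptom/condition for the subject, and results in either self-treatment or treatment by a health care provider".

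The foreseen harms are in E1c. Group discussion or exercises may make participants focus more on their pain, "which may lead to a temporary increase in pain intensity" or distress about it. The EEG assessment may raise overall pain and "may cause a temporary increase in PTSD symptoms". Answering questions about symptoms may temporarily increase their intensity or the distress they cause. Hypnosis may bring back distressing memories.

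On recording, D6j has the EEG technician ask about negative effects "to make certain all adverse events related to the study are recorded". Section 3d has staff log all AEs, with severity, attribution, action taken and outcome.

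On use, the annual report described in 3j asks whether AE rates agree with pre-study assumptions. Under 3h the trial stops if "one of the interventions is associated with adverse effects that call into question the safety of the intervention".

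**The concern.** The two conditions in 3a suit a trial in which the expected harms are new events that need care. Here the expected harms are mostly flare-ups of what participants already have. A rule that admits only new and treated events works against exactly those harms.

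What is at stake is the meaning of a low AE rate. If worsening of pain or PTSD symptoms is not logged as an AE, a low rate partly reflects the documentation rule. It then says little about whether self-hypnosis (HYP), mindfulness meditation (MM) or the EEG procedure made some participants worse. The annual comparison with pre-study assumptions would have the same weakness.

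**Working it through.** No arithmetic applies: the documents state no expected or observed AE rate and no safety sample size. The check is to apply the 3a rule to the named risks and then compare it with the other recording text.

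**Step 1. Apply the rule.** The two conditions give four cases for a non-serious occurrence that meets the AE definition.

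| | Treated or self-treated | Not treated |
|---|---|---|
| New symptom or condition | Documented | Not documented |
| Worsening of an existing one | Not documented | Not documented |

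**Step 2. Place the named risks in the table.**

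- *Increased pain.* Pain at entry is an inclusion criterion in D5: an average of at least 3, a worst of at least 5, and "Experiences pain at least 75% of the time in the past 3 months". An increase in that pain is not new, so it falls in the bottom row even if treated. Pain at a new site or of a new type could count as new.
- *Increased PTSD symptoms.* PTSD is no bar to entry. The psychiatric exclusion reads "Hospitalization for psychiatric reasons other than suicidal ideation, homicidal ideation, and/or PTSD", so even a hospital stay for PTSD is carved out. A1 lists PTSD and mood disorders among prevalent co-morbidities. For a participant with PTSD an increase falls in the bottom row. The number with PTSD at entry is not stated.
- *Distress, including distressing memories under hypnosis.* If distress was already present, this falls in the bottom row. If new, it is documented only when treated.
- *Grogginess, disorientation, or numbness from sitting still.* These may be new, but if they pass without treatment they fall in the top right cell.

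E1c describes the increases in pain and PTSD symptoms as temporary, which makes the untreated column the likelier one.

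**Step 3. Compare with the other recording text.**

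- *The definition in 3a.* It does not require that an occurrence be new or treated. The documentation sentence adds both.
- *Section 3d.* If its reference to all AEs means all that meet the definition, 3a contradicts it. If it means all that pass the 3a sentence, the narrow rule governs the whole AE record.
- *D6j.* The post-EEG question has no such limit and aims at completeness. Two harms it is likely to elicit, more pain and more PTSD symptoms, are ones that 3a often screens out.
- *Section 3b.* The severity scale has a grade for events without major impact. Such events are the least likely to be treated.

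**Step 4. Look for a route that recovers the lost events.**

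- *Serious AEs.* The definition in 3a starts from any AE, and 3e records all of them. Serious worsening can be captured.
- *Self-directed violence.* F1e has its own documentation rule with no new-or-treated condition.
- *EEG negative effects.* Under 3j these go on the EEG recording sheets.
- *Post-session forms.* The risk-protection section passes on reports of a possible AE.
- *Volunteered psychological decline and increased substance use.* 3j has these collected.
- *Charts.* 3j says they will not be monitored for AEs.
- *Outcome scores.* Table 5 schedules the pain rating and the PTSD Checklist at pre-treatment, during treatment, post-treatment and at 3 and 6 months. D6x plans no worsening threshold or safety tabulation for them.

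For the EEG sheets, session forms and volunteered reports, nothing says that non-serious worsening then becomes a logged AE. That decision returns to 3a.

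**The case against.** The strongest reply is that the plan is wider than one sentence of 3a. Serious worsening is recordable, self-directed violence has its own route, EEG effects are asked about and written down, session forms are read, and psychological decline is collected when volunteered. Blinded staff score pain and PTSD symptoms at seven assessment periods, and pain is rated before and after each session. This stands, and it limits the point in three ways.

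- A reader might infer that worsening of pain or PTSD cannot be counted, or has no documentation route at all. The documents do not support that. The data exist; what is missing is a rule that makes non-serious worsening an AE, or a planned analysis that reports it.
- A reader might infer that the AE rate is the trial's only safety outcome and that the stopping rule rests on it. No section says so. Serious AEs, unanticipated serious problems and reasons for dropout are also reviewed, and 3h refers to adverse effects without naming a rate.
- A reader might put a capture rate on the rule, such as zero for pain. The routes above and the possibility of pain at a new site rule that out, and no prevalence or event figure is given.

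A second reply is that 3a says what must be documented and forbids nothing more. On that reading, whether to log a flare-up is left to each staff member, and the counts have no fixed meaning.

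A third is that a threshold for logging mild events in a non-invasive behavioural trial is a legitimate choice. So it is, but this threshold is set at odds with 3d, D6j and E1c, and those sections need to agree.

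**Conclusion.** The concern holds in a limited form. Followed as written, the 3a sentence keeps two kinds of event out of the AE record: non-serious worsening of existing pain, PTSD symptoms or distress, and new psychological reactions that go untreated. Most of the harms foreseen in E1c are of these kinds. The sentence is inconsistent with the definition above it, with 3d on its plain reading, and with the aim in D6j.

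The effect is that AE rates understate these harms. The direction is clear; the size cannot be derived from the documents. The conclusion assumes that staff apply 3a literally and that the EEG sheets and session forms are not converted into AEs by some instruction outside the document. The primary efficacy analysis is not affected. A statement that the interventions are safe would be weakened if it rested on AE counts alone.

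**What to change.** 1. **Reconcile 3a with 3d, D6j and E1c.** Have staff document an occurrence that is new, or is a worsening from baseline of an existing symptom or condition, and that is reported as a negative effect, whether or not it was treated. Treatment stays as a recorded attribute, since action taken is already on the AE form. Requiring that it be reported as a negative effect keeps ordinary day-to-day variation in pain out of the log. State that answers on the EEG sheets and session forms are assessed against the same rule.

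2. **Pre-specify a by-arm tabulation of worsening in the final analysis**, using the pain rating and PTSD Checklist at each assessment period. D6x defines change as pre-treatment minus post-treatment, so worsening is a negative value. Report the distribution by arm and the number beyond a cut-off fixed before unblinding; the documents give none. Comparison with the education arm (ED) separates a treatment effect from natural fluctuation.

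The second step does not replace the first. The pain outcome averages up to four 24-hour ratings within a week, so a brief rise after a session or an EEG can disappear in it. Nor does the first replace the second: the monitoring tables in 3k are pooled over arms. If follow-up is complete, only the tabulation can still be done in full.

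The cost is a change of wording in 3a and the form instructions, one added table, more (mostly mild) AE entries and a higher reported AE rate. No visits or measures are added.

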Participants will report the skills s/he used during this assessment portion, as well as general experience during this portion. Participants will be compensated \$100 for completion of the brain wave activity assessment via a check written from the Seattle Institute for Biomedical and

Clinical Research (SIBCR). The check will be sent via USPS mail and accompanied by a payment cover letter.

Participants may still participate in the study if they decline to participate in the EEG assessments. The EEG assessment is optional.

D6k. Assessment: Pre-Treatment and General Overview

Subjective reports of pain intensity vary over time, and to most accurately measure pain intensity (our primary outcome), it is most valid to assess multiple times and take an average. Hence, we have developed a method of assessment that will seek to obtain up to four telephone assessments over a period of one week or 7 days. In addition, research staff will seek to administer these assessments ideally with a minimum of 24 hours between each assessment. Given scheduling conflicts, research staff may collect each assessment no less than 22 hours between each assessment if necessary.

During *each* telephone contact, research staff will ask participants, at minimum, to rate their current, average, worst and least pain intensity over the past 24 hours, as well as their average pain intensity over the past week.

In addition, if possible, research staff will ask the participant to rate their current, average, worst and least pain intensity over the past week during the final telephone contact. These assessments will be referred to as “short assessments.” The primary outcome will be an average of all of the 24-hour ratings (range=1-4 ratings) of average pain intensity obtained over a period of one week during each assessment period.

In addition, sometime during this assessment period researchers will ask questions regarding pain interference, depression, anxiety, sleep disturbance, post-traumatic stress disorder (PTSD) symptoms, medication use, medical services utilization, thoughts about pain and treatment motivation. This latter set of questions will only be asked once during the assessment period, and will be referred to as “the long assessment.”

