The assessment period described above will be completed prior to initiating treatment, and then after completion of treatment sessions #2, 4 and 6 and 8 (i.e. post-treatment), and 3 and 6 months following the end of treatment for a total of seven times. These assessment periods that occur following the start of treatment will also include questions about group climate, therapeutic alliance with the group clinician, treatment satisfaction, feedback about the treatment modality, and overall improvement since the participant began the pain program. The open-ended questions regarding treatment satisfaction and feedback on treatment modality will be collected by an unblinded staff member. Group Comfort Questions will be administered by an unblinded staff member at any time after session 8 (final group session). This assessment is optional. The window is from post-treatment until the participant is disenrolled.

Staff will send via USPS mail a reminder letter prior to the 3- and 6-month assessment periods.

As mentioned above, during the consent process research staff will provide participants with a response key to help answer questions asked during the telephone assessment periods. Participants may request research staff send another response key to them if they lose the key during study participation. Research staff will send the response key along with a cover letter via USPS mail.

Participants will be compensated \$25 for the completion of each assessment period via a check written from the Seattle Institute for Biomedical and Clinical Research (SIBCR). The check will be sent via USPS mail and accompanied by a payment cover letter.

The pre-treatment assessment period may take place up to four weeks prior to the start of the treatment groups for that particular cohort.

D6I. Randomization

Enrolled participants who complete the required baseline components (cognitive assessment, hypnotic and relaxation exercise, baseline data form, and pre-treatment assessment period) will be randomized in stratified blocks to ensure that participants with each sex/gender and pain type (neuropathic, non-neuropathic, mixed or undetermined) have an equal chance of being randomized to one of the 3 conditions. Stratification will assure that the treatment groups are balanced regarding each stratification variable, so that the estimated effect of the treatment is not biased due to differences in distribution of sex/gender or type of pain.

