The study clinicians moderating the group treatment sessions will disperse forms after each treatment session that asks each participant what they found helpful or unhelpful about the treatment session. We believe these questions will allow participants to express any events that may be adverse and possibly related to study procedures.

General

Research staff and study clinicians will collect unsolicited information reported by participants during study participation including suicidal thoughts or suicidal ideation (SI), increased alcohol/drug use, intentions to harm someone else, or psychological decline.

All information leading to an adverse event (AE), serious adverse event (SAE), or unanticipated problem will be reported per VA protocol/requirement, i.e., to VAPSHCS IRB using the approved VA IRB forms. Reports will be submitted within the designated required time frame (5 business days). In addition, staff members will use templates provided by the study sponsor to capture specific data pertaining to AEs, SAEs, or unanticipated problems. All documentation collected, submitted, and approved will be stored in a regulatory binder located within the locked study offices. We do not plan to monitor charts for AEs.

Study researchers will document any protocol deviations or events that may jeopardize the integrity of the study in a 'Note-to-File' using the sponsor template for this purpose.

Safety information collection will begin as soon as study recruitment begins. Safety information collection will end once the subject completes the final telephone assessment, i.e. approximately six months following completion of the intervention.

Progress Report (Monthly and Quarterly)

Each month research staff will generate a study report that outlines study progress including recruitment, retention/attrition, any protocol deviation or violation that warrants a note-to-file, and AEs, SAEs and unanticipated problems for that particular month. This report will be provided to the Co-PIs. The Co-PIs may solicit input from the chair of the DSMC if they detect anything of concern.

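### Section 3j promises systematic safety monitoring to the final call, but no adverse-event question is specified for any telephone assessment and Appendix 1 schedules no adverse-event contact after post-treatment

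*Combined protocol and SAP*

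**What the plan says.** Section 3j names the people who run the telephone, EEG and cognitive assessments and the classes as collectors of safety information, and states: "By systematically monitoring for events, we will ensure that problems are detected immediately". It ends collection at the participant's final telephone assessment, about six months after the intervention. It then describes these routes:

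- **EEG visits.** Section D6j says: "The EEG technician then will ask each participant whether they experienced any negative effects they associate with study procedures". Section 3j confines the question to effects during the assessment itself. D6j also makes the EEG optional.
- **Classes.** Clinicians "disperse forms after each treatment session that asks each participant what they found helpful or unhelpful about the treatment session".
- **Everything else.** "Research staff and study clinicians will collect unsolicited information reported by participants during study participation".
- **Records.** "We do not plan to monitor charts for AEs".

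Section 3d gives each participant an adverse events form, but no question and no timing. The telephone content in D6k and Table 5 contains no adverse-event item. The Adverse Events row of Appendix 1 is marked at all eight sessions and at the 2-, 4- and 6-week and post-treatment assessments. It is blank at 3 and 6 months.

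**The concern.** The solicited routes do not match the protocol's own definition. Section 3a counts any untoward medical occurrence during participation, documented when it is new and leads to treatment, and it counts an inpatient admission as serious. The class form asks about that session. The EEG question asks about effects linked to study procedures. Neither would elicit an intercurrent illness or an admission, and charts are not searched. What is recorded then depends on being in class, accepting the EEG, or volunteering.

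Delay makes this worse. Section E1c expects that distress from memories under hypnosis may outlast the session, and that grogginess may follow hypnosis or mindfulness. It anticipates no stress or discomfort from education, although it lists discomfort from group discussion for all three conditions. A harm that appears after class reaches a class form only if the person comes back.

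The counts matter. Section 3h would stop the study if an intervention is associated with adverse effects that put its safety in doubt, and the annual report in section 3j must compare adverse-event rates with pre-study assumptions. Both would rest on counts that partly reflect how events came to notice.

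**Working it through.** **1. Telephone contacts.** D6k places one assessment period before treatment, three during it (after sessions 2, 4 and 6), one after session 8, and then "3 and 6 months following the end of treatment for a total of seven times". The count 1 + 3 + 1 + 2 = 7 reproduces the plan's figure. In each period staff "seek to obtain up to four telephone assessments over a period of one week or 7 days", so the maximum is 7 × 4 = 28 calls. Four of these precede treatment, which leaves 28 − 4 = 24 once treatment has started.

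**2. Split by Appendix 1.**
- Periods marked for adverse events: 2, 4 and 6 weeks and post-treatment, 4 × 4 = 16 calls.
- Periods left blank: 3 and 6 months, 2 × 4 = 8 calls.
- Check: 16 + 8 = 24. With the eight sessions, the row has 8 + 4 = 12 marks.

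**3. Calendar.** Appendix 1 puts session 1 in week 3, session 8 in week 10, post-treatment in weeks 11-12 and the final assessment in weeks 34-35. Weeks 3 to 35 inclusive number 35 − 3 + 1 = 33. Weeks after week 12 number 35 − 12 = 23, and 23/33 = 70%.

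**4. What is specified at each contact.**

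| Contact | Marked in Appendix 1 | How events are elicited | Who is reached |
|---|---|---|---|
| Sessions 1-8 | Yes | Helpful/unhelpful form | Those who attend |
| 2-, 4-, 6-week calls | Yes | Not specified | All, including those withdrawn from treatment (D6n) |
| Post-treatment calls | Yes | Not specified | All, as above |
| EEG visits | Post-treatment column only | Question on negative effects | Those who accept the EEG |
| 3- and 6-month calls | No | Not specified | All, as above |

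**5. Side by side.** Section 3j runs safety collection to the last row of the table. Appendix 1 stops it one assessment before that row. Both cannot be followed as written.

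**The case against.** A reader might infer that people who miss or leave class are not asked about harms, and that nobody is asked after session 8. The documents do not support either statement.

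- Appendix 1 schedules adverse events at four telephone assessments, one of them in weeks 11-12. Section 3j names telephone assessors as collectors. D6n invites participants withdrawn from treatment to every later assessment.
- The post-treatment EEG carries its own question, and unblinded staff put open-ended questions on satisfaction and treatment modality (D6k).
- The call scripts and the adverse events form are not in the documents. Silence in D6k and Table 5 shows that no question is specified, not that none is put.
- D6o tracks reasons for treatment withdrawal, the annual report covers reasons for dropout, and the Treatment part of section 2 includes adverse events in clinician supervision.
- Calls collect pain, depression, anxiety and PTSD symptoms in every period, so follow-up is not blind to deterioration.

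All of this stands, but it does not close the gap. Withdrawal reasons and satisfaction questions are not adverse-event queries, and symptom scales do not record admissions. Medical services utilization comes closest, and Table 5 marks it at 3 and 6 months. But D6t describes it as professional care for pain, and outside treatment Table 4 looks back one month. The intervals it would need to span are about 11 weeks (weeks 11-12 to 22-23) and 12 weeks (weeks 22-23 to 34-35).

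Two further inferences should be resisted. The 30% drop-out allowance in D5 is not a count of people lost to the class forms: D5 defines non-completers as never randomized, or randomized with no later data, so someone who leaves class early and answers one later assessment is a completer. And no figure in the documents shows that attendance or EEG acceptance differs by arm or falls among those harmed. That is a possibility only.

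**Conclusion.** The point holds as a gap in specification together with an internal inconsistency. Section 3j claims systematic monitoring, yet outside the classes and the optional EEG it describes only unsolicited reports, and no adverse-event question is specified for any of the up to 24 calls after treatment starts. For up to 16 of those calls Appendix 1 schedules collection without a method. For up to 8 it schedules none, which leaves about 23 weeks, or 70% of the time from first class to last call, without a scheduled adverse-event contact. Admissions and delayed distress may be captured only if volunteered.

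The call counts are maxima, since a period may yield fewer than four calls. The weeks are those of Appendix 1, which notes that enrollment and pre-treatment timing vary. The conclusion concerns what the documents specify, because the scripts and forms are not available. It bears on the safety reporting and leaves the primary pain analysis untouched. It is a worthwhile, inexpensive improvement.

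**What to change.** Add one fixed question to the telephone script at the end of the last call of each of the six assessment periods after treatment starts, after the pain ratings. It should ask about any new or worse health problem, and any hospital or emergency visit, since the last period. Put it to everyone regardless of attendance, and pass positive answers to an unblinded clinician. List the item in Table 5, mark it at 3 and 6 months in Appendix 1, and have section 3j name it as the telephone route, so that the three places agree. If the existing scripts already contain such a question, quote it in section 3j and correct Appendix 1.

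The cost is one script and form item, an IRB amendment, and about a minute per period with the callers already in place: 6 × 1 = about 6 minutes per participant, against 45-60 minutes of questions in each period. The downside is small: an answer may hint at the arm to a blinded caller, which asking last limits.

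If the calls have already ended, report that adverse-event collection was largely unsolicited and had no scheduled contact after post-treatment, and read the counts by arm with that in mind.
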